
2.2. Background

ALXN1840 has been in development for the treatment of WD and PBC due to its improved stability properties over ammonium tetrathiomolybdate, the latter of which has previously been studied in patients with WD and other indications. Ammonium tetrathiomolybdate as well as bis-choline tetrathiomolybdate non-clinical and clinical data reported to date support therapeutic efficacy with an appropriate safety profile for ALXN1840.

ALXN1840 rapidly forms irreversible TPC, which stabilize free and potentially toxic Cu leading to a reduction in the non-ceruloplasmin-bound Cu (NCC) concentrations or NCC corrected for TPC [NCC_{corrected}]) (Weiss, 2017).

Detailed descriptions of the chemistry, pharmacology, efficacy, and safety of ALXN1840 are provided in the IB for ALXN1840.

2.3. Benefit/Risk Assessment

More detailed information about the known and expected benefits and risks and reasonably expected adverse events (AEs) forALXN1840 may be found in the IB and of bupropion in the prescribing information (WELLBUTRIN SR).

2.3.1. Risk Assessment

Details of the potential risks and mitigation strategy are provided in Table 2.

Table 2: Potential Risks and Mitigation Strategy

Potential Risk of Clinical Significance	Summary of Data/Rationale for Risk	Mitigation Strategy
ALXN1840		
Dose-dependent elevations in transaminases (ALT and AST)	Generally mild to moderate in severity, asymptomatic and reversible with dose adjustments were reported, usually after 3 - 6 weeks of treatment in patients with WD	Regular monitoring of liver function tests
Anemia	Anemia has been observed in patients with WD, PBC and cancer, attributed to overtreatment and resultant Cu depletion	Monitoring complete blood count
Low white blood cell count (leukopenia, bone marrow toxicity)	Leukopenia and bone marrow toxicity (myelosuppression) have been observed in patients with WD and attributed to overtreatment and resultant Cu depletion	Monitoring complete blood count
Study Procedures		
Risks associated with the study design and procedures	Participants will undergo repeated blood draws to measure the PK of the study intervention and metabolism. Blood draws may result in ecchymosis, redness and	Blood draws are optimized for PK. A cannula may be placed to minimize needle sticks

	minor pain to the site. On rare occasion, infection or thrombophlebitis can occur	
Bupropion		
As per prescribing information	Bupropion prescribing information (WELLBUTRIN SR)	Participants will be monitored for adverse reactions and by regular laboratory assessments. Participants may be discontinued for significant drug related adverse events

Abbreviations: ALT = alanine aminotransferase; AST = aspartate aminotransferase; Cu = copper; IB = Investigator's Brochure; PBC = primary biliary cholangitis; PK = pharmacokinetics; WD = Wilson Disease.

2.3.2. Benefit Assessment

This is a healthy volunteer study, and there is no direct benefit to study participants.

2.3.3. Overall Benefit: Risk Conclusion

Taking into account the measures implemented to minimize risk to participants, the potential risks identified in association with ALXN1840 and bupropion are justified by the anticipated benefits that may be afforded to patients with WD and PBC.

3. OBJECTIVES AND ENDPOINTS

Objectives	Endpoints
Primary	
To determine the effect of ALXN1840 on the PK of bupropion, a sensitive CYP2B6 substrate	PK parameters of bupropion (C _{max} , area under the plasma concentration (AUC) versus time curve from time 0 to the last quantifiable concentration [AUC _t], and AUC versus time curve from time 0 to infinity [AUC _∞]) with and without the coadministration of ALXN1840
Secondary	
 To determine the effect of ALXN1840 on the PK of hydroxybupropion, the major active metabolite of bupropion To determine the effect of ALXN1840 on the PK of plasma Mo with the coadministration of bupropion To determine the safety and tolerability of ALXN1840, with the coadministration of bupropion 	 PK parameters of hydroxybupropion (C_{max}, AUC_t, and AUC_∞) with and without the coadministration of ALXN1840 PK parameters for plasma total Mo (C_{max}, AUC_t, and AUC_∞) with the coadministration of bupropion Safety assessed by incidence of treatment-emergent adverse events (TEAEs) and treatment-emergent serious adverse events (TESAEs), physical examination, vital signs measurements, clinical laboratory and 12-lead electrocardiogram (ECG) results

Abbreviations: AUC_{∞} = area under the plasma concentration versus time curve from time 0 to infinity; AUC_t = area under the plasma concentration versus time curve from time 0 to the last quantifiable concentration; C_{max} = maximum observed plasma concentration of the drug; CYP2B6 = cytochrome P450 2B6; ECG = electrocardiogram; PK = pharmacokinetics; TEAE = treatment-emergent adverse event; TESAE = treatment-emergent serious adverse event.

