 To determine the effect of ALXN1840 on the PK of hydroxybupropion, the major active metabolite of bupropion To determine the effect of ALXN1840 on the PK of plasma molybdenum (Mo) with the coadministration of bupropion To determine the safety and tolerability of ALXN1840, with the coadministration of bupropion 	 PK parameters of hydroxybupropion (C_{max}, AUC_t, and AUC_∞) with and without the coadministration of ALXN1840 PK parameters for plasma total Mo (C_{max}, AUC_t, and AUC_∞) with the coadministration of bupropion Safety assessed by incidence of treatment-emergent adverse events (TEAEs) and treatment-emergent serious adverse events (TESAEs), physical examination, vital signs measurements, clinical laboratory and 12-lead electrocardiogram (ECG) results

Abbreviations: AUC_{∞} = area under the plasma concentration versus time curve from time 0 to infinity; AUC_t = area under the plasma concentration versus time curve from time 0 to the last quantifiable concentration; C_{max} = maximum observed plasma concentration of the drug; CYP2B6 = Cytochrome P450 2B6; ECG = electrocardiogram; MO = molybdenum; PK = pharmacokinetics; TEAE = treatment-emergent adverse event; TESAE = treatment-emergent serious adverse event

Overall Design

This is a Phase 1, randomized, 2-period, 2-sequence, cross-over study designed to determine the effect of ALXN1840 on the metabolism of bupropion, a sensitive CYP2B6 substrate, in healthy male and female participants. The safety and tolerability of ALXN1840 will be determined along with ALXN1840 PK in plasma as measured via total Mo with the coadministration of bupropion.

Disclosure Statement: This is an open-label, 2-period, 2-sequence, cross-over study in healthy participants with randomization to 2 treatment sequences.

Number of Participants:

It is planned that approximately 52 participants will be enrolled and randomized at a single site.

Intervention Groups and Duration:

The study has a Screening Period (Day -28 to Day -2), two 11-day study periods (Day 1 to Day 11) with a minimum of 14 days between doses of bupropion, and an End of Study (EOS) Visit (Day 15 ± 2 days) after Period 2 dosing. Participants will report to the CRU on the day prior (Day -1) to both dosing periods.

In each study period, participants will receive one of the 2 treatments noted below:

- Treatment A: One 150 mg bupropion HCl salt tablet (WELLBUTRIN SR 150) with 240 mL water (fasting).

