- Treatment B: One 150 mg bupropion HCl salt tablet (WELLBUTRIN SR 150) + 4 × 15 mg ALXN1840 EC tablets with 240 mL water (fasting).

Participants will receive each treatment as a single dose administration in the sequence as defined below.

Sequence number	Treatment sequence		Total
	Study Period 1	Study Period 2	
1	A	В	26
2	В	A	26
Total			52

Treatment A -One 150 mg bupropion HCl salt tablet (WELLBUTRIN SR 150) with 240 mL water (fasting) Treatment B – One 150 mg bupropion HCl salt tablet (WELLBUTRIN SR 150) + 4 × 15 mg ALXN1840 enteric-coated tablets with 240 mL water (fasting)

The time between dosing bupropion alone or in combination with ALXN1840 in each treatment sequence will be a minimum of 14 days. Based on the estimated mean ALXN1840 half-life of approximately 2 days in healthy participants (under oral dose of 60 mg), a 14-day period between doses of bupropion is considered sufficient to eliminate, on average, approximately more than 99.2% of the plasma total Mo before the next dose of bupropion is administered. The mean elimination half-life (±SD) of bupropion after chronic dosing is 21 (± 9) hours (WELLBUTRIN SR). A 14-day period between doses of bupropion is sufficient to eliminate, on average, more than 99.2% of the plasma bupropion before the next dose of bupropion is administered.

Participants will return to the CRU on Day 15 (\pm 2 days) following Period 2 dosing for the EOS Visit with follow-up procedures, and to determine if any adverse events (AEs) have occurred since the last study visit. If participants withdraw from the study early, they will be seen and assessed by the Principal Investigator, and whenever possible, they are to undergo the procedures associated with the EOS Visit. Participants may be replaced at the discretion of Alexion.

[figure not shown]
Participants may be asked or required to stay in the CRU between Periods 1 and 2, and/or before the EOS visit, for their own safety, and also to maintain the integrity of the conduct of the study.

Data Monitoring Committee:

There will not be a Data Monitoring Committee, but provision is included for an ad hoc Safety Review Committee, if needed.

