4. STUDY DESIGN

4.1. Overall Design

The study is being conducted as a randomized, 2-period, 2-sequence, cross-over study to determine the effect of a single dose of ALXN1840 (perpetrator) on the single dose bupropion (victim) kinetics in healthy male and female participants.

The study has a Screening period (Day -28 to Day -2), two 11-day study periods (Day 1 to Day 11) with a minimum of 14 days between doses of bupropion, and an End of Study (EOS) Visit (Day 15 ± 2 days) after Period 2 dosing. Participants will report to the clinical research unit (CRU) on the day prior (Day -1) to both dosing periods.

All participants will receive 1 treatment in each study period; treatment order will be defined based on randomization:

- Treatment A: One 150 mg bupropion HCl salt tablet (WELLBUTRIN SR 150) with 240 mL water (fasting).
- **Treatment B**: One 150 mg bupropion HCl salt tablet (WELLBUTRIN SR 150) + 4×15 mg ALXN1840 EC tablets with 240 mL water (fasting).

Based on randomization, participants will be administered either Treatment A or Treatment B in each period. A wash-out period of at least 14 days must separate dose administration in Period 1 and Period 2. Participants will remain institutionalized from the day prior to dosing until Day 11 following dose administration for each period.

The PK profile of ALXN1840 and bupropion will be determined by blood sampling following single dose administration over approximately 5 half-lives or more for both study interventions. Blood sampling for PK assessments will occur at pre-dose, 1, 2, 3, 4, 5, 6, 8, 12, 24, 48, 72, 96, 120, 144, 168, 192, 216, 240, and 336 hours post-dose to ensure full assessment of exposure over time. The nominal 336-hour sample for Period 1 is pre-dose sample for Period 2. In addition to PK sampling, safety and tolerability will be assessed by monitoring AEs, vital signs, 12-lead electrocardiograms (ECGs), and laboratory parameters.

Following scheduled procedures on Day 11, participants will be discharged from the unit. If there are any participants with clinically significant abnormalities at the time of discharge, the Investigator should notify the Medical Monitor prior to discharge, and participants may be asked to remain institutionalized for further clinical monitoring.

Participants may be asked or required to stay in the CRU between Periods 1 and 2, and/or before the EOS visit, for their own safety, and also to maintain the integrity of the conduct of the study.

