4.3. Justification for Dose

ALXN1840

The maximum tolerated dose (MTD) of ALXN1840 is unknown. To date, the 60 mg single dose and repeated daily doses have shown a good safety profile and were well tolerated throughout the Phase 1 to Phase 3 clinical studies. The 60 mg dose is well within the dose range demonstrated to have a good safety profile in studies in healthy volunteers and patients with WD. The 60 mg dose is well within the dose range to have an acceptable safety profile in humans as

demonstrated in the completed bioavailability studies that were conducted in healthy male and female participants (Study WTX101-101 and Study WTX101-102) with a median (range) body weight of 80.8 kg (57.6 to 107.0 kg) as well as the completed Study WTX101-201, conducted in patients with WD.

Tetrathiomolybdate reacts with albumin-bound Cu in the liver or blood to form a stable tripartite complex which is excreted into the bile. Tetrathiomolybdate which does not bind to Cu and albumin, is not metabolized by the liver but undergoes hydrolysis to form molybdate anion, which is excreted in the urine. Therefore, findings from the human microsome study (Study CYP0840-R2) are considered an over-estimation of the effect to be observed in vivo. Given that in vitro inhibition was observed with the ALXN1840 parent drug and no apparent accumulation of free ALXN1840 as part of the plasma ultrafiltrate (PUF) Mo or non-TPC-bound Mo after ALXN1840 repeated dosing (preliminary results from Study WTX101-201), a single dose of ALXN1840 is considered to be sufficient to assess the inhibition potential of CYP2B6 using bupropion as the substrate. Single dose administration of the ALXN1840 tablet under fasted conditions resulted in a peak drug concentration of total Mo at approximately 4.54 hours, with a half-life of approximately 51 hours (Study WTX101-102).

Bupropion

Bupropion is extensively metabolized in humans. Following oral administration of 150 mg of 14C-bupropion in humans, 87% and 10% of the radioactive dose were recovered in the urine and feces, respectively. The fraction of the oral dose of bupropion excreted unchanged was only 0.5%, a finding consistent with the extensive metabolism of bupropion (WELLBUTRIN SR).

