8.3.6. Retained and Biobanked Sample

A single biobanked serum sample will be collected pre-dose to serve as a retained safety sample during the study. At the end of the study, pre-dose safety samples will be biobanked to support assay development and determination of normal Cu and Mo levels in healthy participants. Samples may be stored and used for up to 5 years following completion of the study.

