9.4.3. Other Analyses

9.4.3.1. Pharmacokinetic and Pharmacodynamic Analyses

Pharmacokinetic analyses will be performed using the PK/PD Analysis Set.

Blood samples for PK analysis of total Mo (as a measure of ALXN1840), bupropion and its metabolite, hydroxybupropion will be collected at the following time points: pre-dose and post-dose at 1, 2, 3, 4, 5, 6, 8, 12, 24, 48, 72, 96, 120, 144, 168, 192, 216, 240, and 336 hours in each period (Note: the 336 hours sample in Period 1 will be collected during the Period 2, Pre-dose [Day 1] Visit).

The following plasma PK parameters will be calculated as endpoints for total Mo, bupropion and hydroxybupropion using noncompartmental methods with Phoenix WinNonlin (Certara USA Inc., Princeton, New Jersey) Version 8.0 or higher or SAS Version 9.3 or higher (SAS Institute Inc., Cary, North Carolina), as applicable. Calculations will be based on the actual sampling times recorded during the study.

- Time delay between the time of dosing and time of appearance of drug concentration in plasma (T_{lag}; for plasma total Mo with ALXN1840 administration)
- Maximum observed concentration in plasma (C_{max})
- Time to $C_{max}(T_{max})$
- Area under the plasma concentration (AUC) versus time curve from time 0 to the last quantifiable concentration (AUC_t)
- AUC versus time curve from time 0 to infinity (AUC∞)
- AUC extrapolated from time t to infinity as a percentage of total AUC_∞ (%AUC_{extrap})
- Apparent terminal-phase elimination rate constant (λ_z)
- Terminal elimination half-life (t_{1/2})
- Apparent oral clearance (CL/F)
- Apparent volume of distribution (V_d/F)
- Metabolite to parent ratio based on AUC (MRAUC) and C_{max} (MRC_{max}) [estimated for bupropion and hydroxybupropion]

Additional plasma PK parameters may be calculated if deemed appropriate.

Plasma concentrations of total Mo, bupropion and hydroxybupropion and time deviation data will be presented in a data listing by participant. Plasma concentration data will be summarized

separately by analyte and time point for each treatment using the following descriptive statistics: number of participants, arithmetic mean, SD, coefficient of variation (CV), median, minimum, and maximum. Mean plasma concentration versus scheduled time profiles will be presented in figures on both linear and semilogarithmic scales. Individual plasma concentration versus actual time profiles will be presented similarly.

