9.3. Pharmacokinetic/Pharmacodynamic Data Presentation Conventions

PK and PD concentration data will be summarized using descriptive statistics (number of participants (N), number of participants with available data (n), arithmetic mean, SD, arithmetic CV, geometric mean (GM), geometric CV, median, minimum and maximum).

The predose PD concentration will be used as baseline; absolute change from baseline will be calculated as: a postdose concentration value – baseline concentration value; percent change from baseline will be calculated as: ([a postdose concentration value – baseline concentration value] / baseline concentration value) $\times 100\%$.

The following conventions will be applied to PK/PD presentations and summaries.

• For continuous variables, all mean and median values are formatted to one more decimal place than the measured value. Standard deviation values are formatted to two more decimal places than the measured value. Minimum and maximum values are presented with the same number of decimal places as the measured value.

• Date variables are formatted as DDMMMYYYY for presentation. Time is formatted in military time as HH:MM for presentation.

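### SAP 9.4 derives plasma molybdenum PK parameters without subtracting endogenous molybdenum, and the Treatment A molybdenum and copper summaries pool ALXN1840-naive with post-ALXN1840 participants (minor)

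*Protocol*

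**What the plan says.** Protocol section 3 lists the secondary objective "To determine the effect of ALXN1840 on the PK of plasma Mo with the coadministration of bupropion". Its endpoint is total Mo Cmax, AUCt and AUC∞ under co-administration. The with-and-without contrast used for bupropion and hydroxybupropion is absent here. The Overall Design in the Synopsis puts the aim descriptively, as "ALXN1840 PK in plasma as measured via total Mo with the coadministration of bupropion".

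SAP 9.4 derives Cmax, Tmax, AUCt, AUC∞, λz, half-life, CL/F, Vd/F and Tlag for total and plasma-ultrafiltrate (PUF) Mo. It specifies no baseline correction. For CL/F and Vd/F it converts the 60 mg dose to 13.31 mg of Mo.

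Two other places show that a background level was in mind. Protocol 8.3.6 plans to use retained samples for "determination of normal Cu and Mo levels in healthy participants". For copper, SAP 9.3 states "The predose PD concentration will be used as baseline" and defines change from baseline, which SAP 9.7 carries into the copper parameters. The only rule that touches pre-dose Mo is in SAP 9.2: for parameter calculation, values below the limit of quantification before the first measurable one become zero, and later ones become missing.

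Protocol 9.4.3.1 samples Mo in both periods and summarises concentrations "separately by analyte and time point for each treatment using the following descriptive statistics". Neither document splits these summaries by sequence.

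**The concern.** Total Mo is the trial's measure of ALXN1840, but a healthy person has Mo in plasma without the drug. If that background is quantifiable, every post-dose value is drug-derived Mo plus a floor. The floor matters little near the peak. Late in the profile it flattens the terminal slope, which lengthens the apparent half-life and enlarges the extrapolated area. CL/F then divides a drug-only dose by an area that includes Mo not from the dose, so it is too low. Tlag, meant as the time when drug first appears, carries no information if Mo is already measurable before dosing.

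The second issue is the Treatment A summary. Sequence AB receives A in Period 1, never having had ALXN1840 (prior exposure is an exclusion criterion). Sequence BA receives A at least 14 days after ALXN1840. One column holds both states. For copper, the BA Period 2 pre-dose baseline is itself a post-ALXN1840 value.

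At stake is the accuracy of a descriptive secondary endpoint and of Mo half-life and clearance estimates that others may reuse. No decision criterion in this trial depends on them.

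**Working it through.** **Inputs from the documents.** Mean Cmax 3.92 µM after 60 mg fasting (protocol 2.1); Tmax 4.54 h, "with a half-life of approximately 51 hours" (protocol 4.3); the protocol sampling times to 336 h; Mo molecular weight 95.95 and ALXN1840 432.54 (SAP 9.4); linear trapezoidal rule (SAP 9.4).

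**Assumptions.** Constant endogenous Mo, b = 0.5, 1, 2 or 5 ng/mL, quantifiable; one-compartment profile; absorption lag 0 or 1 h; terminal fit on the last 3, 4 or 5 points. None of these is in the documents.

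**Step 1: the plan's own figures.**
- Mo dose: 95.95/432.54 × 60 = 13.31 mg, as stated.
- Washout at 48 h: 1 − 2^(−336/48) = 1 − 2^(−7) = 99.22%, which reproduces the stated 99.2%.
- Washout at 51 h: 1 − 2^(−336/51) = 98.96%.

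**Step 2: units.** 3.92 µM × 95.95 = 376 ng/mL.

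**Step 3: effect of leaving b in (Treatment B, true half-life 51 h, lag 1 h, 5-point fit).** The drug-only profile has AUCt about 28,990 ng·h/mL and is down to about 4.2 ng/mL at 336 h. The floor adds b × 336 to AUCt, for example 5 × 336 = 1,680, and 1,680/28,990 = 5.8%.

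| b (ng/mL) | Half-life (h) | Half-life bias | AUCt bias | AUC∞ bias |
|---|---|---|---|---|
| 0.5 | 53.4 | +5% | +0.6% | +0.8% |
| 1 | 55.8 | +9% | +1.2% | +1.5% |
| 2 | 60.4 | +18% | +2.3% | +3.1% |
| 5 | 73.2 | +44% | +5.8% | +8.0% |

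With a 3-point fit, half-life at 5 ng/mL is about 80 h (80/51 = 1.57, so +57%). Changing the lag makes almost no difference. Half-life is the sensitive parameter because the last sample, about 4.2 ng/mL of drug-derived Mo, is of the same order as the assumed floor.

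**Step 4: derived parameters.**
- Cmax: 0.5/376 = 0.1% to 5/376 = 1.3% high.
- CL/F = dose/AUC∞: 1/1.008 = 0.992 to 1/1.08 = 0.926, so 0.8% to 7.4% low.
- Vd/F = (CL/F)/λz is proportional to CL/F × half-life: 0.992 × 53.4/51 = 1.04 to 0.926 × 73.2/51 = 1.33, so 4% to 33% high with the 5-point fit.

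PUF Mo cannot be sized, because the documents give no PUF concentrations.

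**Step 5: residual Mo when BA participants start Treatment A.** 3.92 × 2^(−(336 − 4.54)/51) = 0.0433 µM, and × 95.95 = 4.2 ng/mL. Against the Treatment B peak this is 0.0433/3.92 = 1.1%. Against the assumed endogenous level it runs from 4.2/0.5 = 8.4 times to 4.2/5 = 0.84 times. At a 48 h half-life the residual is 0.0327 µM, or 3.1 ng/mL.

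**Step 6: is the Treatment B pre-dose sample a clean baseline?** Yes. BA participants receive B first, AB participants have had only bupropion before it, and prior ALXN1840 or other tetrathiomolybdate is excluded.

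**The case against.** The strongest reply is that the size rests on inputs the documents lack. The endogenous level, assay limit, profile shape and terminal-fit rule are all assumed. Protocol 8.3.6 concerns a stored serum sample and does not show that the plasma assay can quantify endogenous Mo. If pre-dose Mo is below the limit, SAP 9.2 sets it to zero and the correction changes nothing; with a low limit, whatever background remains is small. This stands and makes the finding conditional.

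The named endpoints also move little: Cmax by at most 1.3% and the AUCs by at most about 8% at the top of the assumed range. Half-life, where the bias is largest, is not a named endpoint. The correction has a cost too: an error of 0.5 ng/mL in one low pre-dose value is 0.5/4.2 = 12% of the drug-derived level at 336 h. These points stand and keep the severity minor.

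On Treatment A, no Mo contrast with A is planned, the BA residual is measured directly (the Period 1 336-hour sample is the Period 2 pre-dose sample), and SAP section 4 lists data by sequence and participant. The split is therefore for clarity.

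Two stronger readings are tempting and should be resisted.
- A reader might infer that the Mo objective cannot be answered because there is no ALXN1840-alone period. That design feature prevents estimating an effect of bupropion on Mo, but the objective does not ask for one. The endpoint is a descriptive Mo profile, Treatment B supplies it free of ALXN1840 carry-over in both sequences, and the mixed model in SAP 9.5 covers only bupropion and hydroxybupropion.
- A reader might infer from 98.96% that the washout statement is wrong. It is hedged as approximate and on average, and rests on a half-life of about 2 days drawn from two studies; 51 h comes from one of them and may itself be uncorrected. The gap is rounding.

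**Conclusion.** The concern holds as a minor, conditional one. SAP 9.4 leaves endogenous Mo in the Mo parameters while the same SAP corrects copper for its pre-dose level, and no reason is given for the difference.

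If endogenous Mo is quantifiable at an assumed 0.5 to 5 ng/mL, half-life is about 5% to 57% too long, depending on the level and the number of terminal points. AUC∞ is about 0.8% to 8% too high, AUCt about 0.6% to 6% too high, CL/F correspondingly low, and Tlag uninformative. If pre-dose Mo is below a low assay limit, the bias largely disappears.

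Pooling Treatment A across sequences adds a residual of about 1% of Cmax in BA. This is negligible beside Treatment B but possibly comparable to the endogenous level that the column would otherwise show. The primary bupropion analysis is unaffected, and the documents do not support a claim that the Mo objective is unanswerable.

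**What to change.** 1. In SAP 9.4, add total and PUF Mo parameters for Treatment B computed after subtracting the same period's pre-dose concentration, and report the uncorrected values alongside. State that the two coincide when pre-dose Mo is below the limit of quantification.
2. Add a rule for corrected values at or below zero, for example excluding them from the terminal fit.
3. Say how Tlag is handled when pre-dose Mo is quantifiable.
4. Summarise Treatment A Mo and copper by sequence, with AB Period 1 as the ALXN1840-free reference.
5. Optionally, reword the objective to match the Overall Design: total Mo PK of ALXN1840 given with bupropion, with no inference about bupropion's effect on Mo.

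Cost: one set of derived variables, one handling rule and one table split, made before database lock. All the samples are already scheduled. The drawback is added noise from relying on a single low pre-dose value, which is why the uncorrected results should stay in the report.
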